**Background and Justification:**

Contracture is defined as a limitation of the maximum passive range of motion (ROM) of a joint due to shortening and changes of periarticular soft tissue structures; including tendons, muscles and ligaments. Once a contracture is present, management options are limited and mainly includes surgery. Contracture contributes to the increased disability, decreased functional ROM, decreased functional activities of daily living and increased pain. The incidence of contracture one year after spinal cord injury has been reported to be as high as 66%, including 33% in elbow and forearm and 41% in wrist and hand. It may be present in up to 28% of patients within 3 months after stroke with wrist as the most affected joint. At 6 months, the incidence increases to 50%.

Contracture is not just limited to spasticity. It is seen in many neurodegenerative and musculoskeletal conditions and is most commonly found in the nursing home population, with a prevalence of 61.2% in older adults in nursing homes in the United States. In Germany, contractures were also seen in 55% of nursing home residents with significant medical and functional consequences. In France, 8.8% of older adults in nursing homes had a claw hand from contracture of wrist or finger flexors (claw hand).

While contracture can be the primary cause of severe pain, the presence of pain and loss of dexterity significantly contribute to the development of the contracture. Thus, pain management is a crucial part of contracture treatment. There are many guidelines for pharmacological and non-pharmacological treatment of contracture and associated pain such as botulinum toxin injection, physiotherapy, stretching, positioning and surgery. While surgery has been recommended as the most effective treatment, it requires to be done under general anesthesia and in an in-patient setting, which impose many risks to patients especially in frail older population most likely to require contracture management.

Our group have been global pioneers in the use of cryoneurolysis to manage spasticity and pain due to severe spasticity and contracture. (clinicaltrials.gov NCT04670783, NCT05147441, NCT04907201). The process first involves isolating the targeted nerves that innervate the targeted muscles with ultrasound guidance (US) and e-stimulation (e-stim) for motor nerves and mixed motor sensory nerves for pain. We are completing enrollment on four studies with over 100 patients enrolled, in both the outpatient and in-patient settings. Our published protocol shows a unique goal for cryoneurolysis, to both decrease the tone and pain. The 2019, French Clinical guideline for peripheral motor nerve blocks in a PRM setting, established the first expert opinion paper for utilizing the DNB in spasticity and pain management. Through temporary paralysis of a muscle by blocking the motor branches of the nerve and blocking the sensory fibers by targeting the sensory fibers of related nerve, the DNB can result in reduction of pain and muscle tone even in what may have been thought to be a fixed contracture. The French guidelines claim the DNB forms the basis of optimal muscle selection and whether to proceed to BoNT, neurectomy, or for a more refractory muscle for surgical muscle lengthening.

In our protocols, after a successful DNB to reduce pain and the muscle tone, a patient is offered cryoneurolysis. This mini-invasive percutaneous procedure is performed using a small 20-gauge cryoprobe. Cryoneurolysis has been used for over fifty years for pain relief from months to years when used for sensory nerves. Cryoneurolysis occurs due to the process of throttling a gas through an orifice from high to low pressure resulting in a rapid expansion of the gas and a drop in temperature, known as the Joule-Thomson effect. The rapid cooling generates an ice ball or oval between 3.5 and 18 mm that is formed at the tip of the with compressed N2O at temperatures typically at -88° C. The ice causes a targeted zone of axon and myelin disruption, resulting in loss of axon continuity due to Wallerian degeneration of the targeted nerve extending outward from the lesion. However, the basal lamina, epineurium and perineurium of the targeted nerve remain intact and serve as a tube for neural regeneration. For over four years we have been tracking outcomes of cryoneurolysis. Our initial results are published as cases but are also in pre-publication prospective studies revealing significant pain reduction. We have published several manuscripts on cryoneurolysis. Several book chapters and a textbook are in in publication or published. Cryoneurolysis is cheaper, faster, and less invasive than surgical intervention for the treatment of severe spasticity and contracture associated pain.

In Canada, one vial of BoNT costs approximately \$400. The typical patient can be injected with 400 units up to four times a year, thus \$6400 a year, indefinitely. Patients are often treated outside the product monograph, off label, with 600 units, and for over ten years, thus treatments may cost many tens of thousands of dollars. A one-time treatment with cryoneurolysis would cost approximately \$725 and could potentially last for years, more in line with surgical neurectomy or tendon lengthening, yet with no recovery time surgery.

After witnessing the reduction in pain from contracture with cryoneurolysis in our experience, we propose to measure its effect prospectively and systematically on pain reduction in patients with wrist and hand severe spasticity or contracture due to any underlying disease. These patients are already undergoing cryoneurolysis in our clinic, with our island health allotment of cryoneurolysis equipment as well as those that were enrolled in our now completed upper extremity study. All patients are deemed candidate for cryoneurolysis based on their positive responses to DNB.

## **Purpose:**

The purpose of this pilot study is to evaluate if cryoneurolysis will be effective to control pain in patient with wrist and hand contracture. Also, to evaluate if there is any correlation between pain reduction with improvement in ROM and spasticity reduction in participants who are already candidate for DNB and cryoneurolysis. The results will increase our knowledge about cryoneurolysis and if it can be used just for pain control and in patients with fixed contracture.

## **Objectives:**

1. To evaluate the effect of cryoneurolysis on pain in patients with hand and wrist contracture.
2. To assess any changes in wrist and fingers ROM and spasticity in patients with hand and wrist contracture.
3. To evaluate if there is any correlation between changes in ROM and spasticity with pain
4. To record any changes in pain medication that they receive for pain management.

## **Hypotheses:**

1. Cryoneurolysis can be used as a pain control tool in patients with wrist and hand contracture.
2. Cryoneurolysis can improve wrist and finger ROM and spasticity in patients with hand and wrist contracture.
3. Pain reduction after cryoneurolysis is independent from the increase in ROM and spasticity reduction.
4. The needs for pain medication will decrease after the procedure.

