### **Statistical Analysis:**

A convenience sample of  $n = 25$  patients will be included in this study. This is consistent with existing volumes of consultations to our clinics. Study recruitment will include all patients with wrist and hand contracture that are considered for cryoneurolysis. The outcome measures that we will use are standard clinical measures, but effect sizes are not readily available from previous studies to formally calculate sample size. Furthermore, our study uses an exploratory prospective cohort design, rather than a parallel group trial design, limiting the rationale for providing a sample size calculation.

To assess for statistical significance, a paired t-test on the difference of proportions, applicable to pre-treatment and post-treatment, will be performed. We will employ repeated measures or linear mixed (multilevel) models of change to analyze within-person trajectories in all key outcomes for the intensive repeated measures data spanning the 4-month study period. Such models derive individual parameter estimates for baseline function and change pursuant to nerve or surgical procedure and will directly index the magnitude in improvement for each outcome with everyone serving as their own control (i.e., with change indexed relative to everyone's own personal baseline). If normal distribution in the outcomes does not stand, McNemar's test and

Spearman correlations will be calculated instead of paired t-test and Pearson's correlation, respectively.

The correlation between range of motion and pain score will be reviewed by Pearson's correlation and or Spearman's rank correlation at single time point. The improvement of range of motion or pain scores during two visits will be compared by two sample t test or Wilcoxon rank sum test.

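### Hypothesis 3 predicts no association between pain relief and change in ROM or spasticity; a correlation in 25 patients can refute that prediction but cannot support it

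*Protocol*

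**What the plan says.** Protocol, Hypotheses, item 3, gives the expected result as: "Pain reduction after cryoneurolysis is independent from the increase in ROM and spasticity reduction".

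Protocol, Objectives, item 3, puts the same question neutrally: "To evaluate if there is any correlation between changes in ROM and spasticity with pain". The Purpose section is also neutral, and adds that the results will inform whether the procedure has a use for pain alone and in fixed contracture.

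Protocol, Statistical Analysis, names one tool for this question: "The correlation between range of motion and pain score will be reviewed by Pearson's correlation and or Spearman's rank correlation at single time point". On size it says "A convenience sample of $n = 25$ patients will be included in this study", and explains that "effect sizes are not readily available from previous studies to formally calculate sample size". The same section calls the design exploratory. Neither the hypotheses nor the statistical section gives a largest correlation that would still count as independence, or a confidence-interval criterion.

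**The concern.** Hypothesis 3 is the null hypothesis of the only analysis attached to it. A large observed correlation would speak against it. The only result that could look like support is a correlation that is small or not significant, and in a small sample that is common even when a real association exists.

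At stake is the interpretation the Purpose section points to. If pain relief appears unrelated to movement and tone, readers may take this as evidence that the procedure relieves pain by a separate route. With 25 patients, a null-looking result would not distinguish that from a moderate association that was missed.

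**Working it through.** **Inputs.** n = 25 (Protocol, Statistical Analysis). No significance level, effect size, power target or margin is stated, and the sample size rests on clinic volume, so there is no planned figure to reproduce. I assume two-sided 5%.

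**1. Smallest significant correlation.** With t(0.975, 23 df) = 2.069, the critical |r| = t / sqrt(t² + n - 2) = 2.069 / sqrt(4.28 + 23) = 0.396.

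**2. What an observed r of 0 would show.** The Fisher z interval is tanh(atanh(r) ± 1.96 / sqrt(n - 3)). With n - 3 = 22 and sqrt(22) = 4.690, the half-width at r = 0 is tanh(1.96 / 4.690) = tanh(0.418) = 0.395. The 95% interval is about -0.40 to +0.40. The 90% interval is ± tanh(1.645 / 4.690) = ± 0.337.

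**3. Power for one correlation.** Power = Φ(atanh(r)·4.690 - 1.96) + Φ(-atanh(r)·4.690 - 1.96). For r = 0.3: atanh(0.3) = 0.3095, times 4.690 = 1.452, and Φ(-0.508) = 0.306 (the second term is negligible).

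| True r | Power, Fisher z | Power, simulated (100,000 runs) | Missed (simulated) |
|---|---|---|---|
| 0.3 | 0.306 | 0.314 | about 69% |
| 0.4 | 0.511 | 0.525 | about 48% |
| 0.5 | 0.731 | 0.750 | about 25% |

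**4. Where the design can refute independence.** 80% power is reached at r = tanh((1.96 + 0.8416) / 4.690) = 0.535, or about 0.54.

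**5. Whether a margin would help.** A 95% interval centred on 0 that lies inside ± 0.3 needs n = (1.96 / atanh(0.3))² + 3 = 43.1, so 44. A formal equivalence test (two one-sided 5% tests, 80% power, true r = 0) needs n = ((1.645 + 1.282) / atanh(m))² + 3.

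| Assumed margin m | n for 80% power | Power at n = 25 |
|---|---|---|
| 0.2 | 212 | 0% |
| 0.3 | 93 | 0% |
| 0.4 | 51 | 27% |
| 0.5 | 32 | 65% |

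The margins are my assumptions. At n = 25 no margin below about 0.34 (90% interval) or 0.40 (95% interval) can be met, whatever the data show.

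**6. Fewer patients per pain scale.** Pain is scored on the NRS or, for patients who cannot self-report, on the CNPI (Protocol, Methods, item 3). A correlation on one scale therefore uses fewer than 25 patients if both scales are used. The split is not given. If 15 patients were on one scale (assumed), the 95% interval at r = 0 would be ± tanh(1.96 / sqrt(12)) = ± 0.51.

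**The case against.** **The faulty inference is not written down.** This stands. A reader might infer that the authors will treat a non-significant correlation as proof of hypothesis 3, but no sentence says so, and the objective and purpose are neutral. The words "To assess for statistical significance" open a sentence about the paired pre- and post-treatment comparison. They do not attach a test or decision rule to the correlation, which comes in a later paragraph. How the authors would write up a null result cannot be predicted from the document.

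**The plan can find a correlation.** This also stands. It would be wrong to say that the plan can only fail to find one, since a correlation of about 0.54 has 80% power and would contradict the hypothesis.

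**The miss rates are for one correlation.** This is correct. Methods item 1 lists seven joint measures, and the statistical section picks none of them. If all seven were tested unadjusted at one visit, with correlations of 0.5 to 0.7 between them (assumed), simulation gives a true 0.3 missed on every measure in about 27% to 37% of studies, and a true 0.4 in about 9% to 17%. With no true association, at least one would be significant in about 18% to 24%. So a general bias of the plan toward independence is not established. The width of each interval is unchanged, and so is the inability to support independence.

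**Noise and selection.** A reader might infer that measurement error and the choice of nerve-block responders shrink the correlation further by a known amount. The protocol gives no reliability figures and no response threshold, and selection does not pull a correlation toward 0 under every rule. I place no weight on this.

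**A SAP may settle interpretation.** A margin or interval rule can be left to a SAP. The wording of the hypothesis and the 25 patients are fixed in the protocol, however, and step 5 shows which margins that number rules out.

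**It is a pilot.** This lowers the severity. It also favours an estimation aim over a hypothesis of no association.

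**Conclusion.** The point holds at moderate severity. Hypothesis 3 states a null that the design can refute if the association is strong but cannot support. The main evidence is the interval of about -0.40 to +0.40 at an observed correlation of 0, which depends only on n = 25 and the usual normal approximation. The critical value, the miss rates and the 0.54 also assume a two-sided 5% level, and the miss rates apply to one correlation at a time.

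The stronger reading, that the protocol commits itself to taking non-significance as proof, is not supported by its text. What is supported is narrower: as worded, the hypothesis has no valid route to confirmation in this plan.

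A separate defect is that the planned correlation is taken at a single time point and names ROM only, whereas the hypothesis concerns changes and includes spasticity. Correcting that would leave the present point untouched.

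**What to change.** Replace hypothesis 3 with an estimation statement, for example: *The association between change in pain and change in (a) ROM and (b) MAS will be reported as a correlation with 95% CI; a non-significant correlation will not be interpreted as independence.*

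Add that the study will report only the range of associations compatible with the data, and only for patients who responded to the diagnostic block, since "All patients are deemed candidate for cryoneurolysis based on their positive responses to DNB". I would not add a claim of independence within a margin: ± 0.3, for instance, which is my assumption, cannot be reached with 25 patients.

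The cost is two sentences in the protocol. Patients, visits, measurements and care stay as they are. The study gives up a conclusion that it could not have supported.

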## **Research Design:**

This project constitutes a single-centre, prospective cohort study. Data collection will occur at the Victoria General Hospital (VGH) spasticity clinic. Patients with severe spasticity and contracture are referred to this clinic for different procedures including cryoneurolysis. This study will not interfere or change the patients' medical care. We will do the assessments for the patients who are already candidates for this procedure as a

Effect of the cryoneurolysis on pain and positioning in patients with wrist and hand contracture. 4

Protocol: [H22-03181]

Version 1.1

Jan 9,2023

part of their treatment, besides other provided medical cares and have been accepted to receive it.

All measurements are a part of routine assessment for patients with severe spasticity and contracture.

The evaluation will be done for them after receiving oral and written consent.

### **Methods:**

The assessment will be done at baseline, 2 weeks, 1 month and 3 months after being enrolled in the study in the same day of their appointments with [name] and includes;

1. Passive and any active range of motions (ROM) of wrist, second and fifth MCP and PIP joints and thumb palmar and radial abduction will be measured by goniometer. Spasticity will be measured based on Modified Ashworth Scale (MAS).
2. The maximum distance between the pulp of the most flexed finger and thumb and the palm of the hand will be measured in centimeter. This distance will be measured during maximal passive extension of the fingers and thumb while the assessor keep the wrist in neutral (or as close to neutral as possible )position.
3. Intensity of pain in the wrist and hand area will be measured by NRS (numerical rating scale), for patients with sufficient cognitive capacity. In this test patients will be asked to score their pain on scale of 0 to 10. Patients who cognitively are not able to score their pain will be assessed by CNPI scale (Checklist of Nonverbal Pain Indicators). In this scale the patient will be observed at rest and during any movement and any nonverbal vocal complaints, facial grimaces, bracing, restlessness, rubbing of the affected area and verbal vocal complaints will be scored accordingly. PI will decide which one of these 2 methods is applicable, based on their assessments, patients' record and in consult with their caregivers.
4. Goal Attainment Scale (GAS): This is a patient-oriented scale to deliver the patient their desired outcomes. Up to 3 individualized, SMART (specific, measurable, achievable, realistic and timed ) goals will be negotiated between participants, caregivers and their physician. At the final visit, they will be asked if they are satisfied with each of these goals and the response will be scored accordingly.

Effect of the cryoneurolysis on pain and positioning in patients with wrist and hand contracture. 5

Protocol: [H22-03181]

Version 1.1

Jan 9,2023

5. Hand hygiene: the evaluator will assess the patients' hands to determine the extent of palm maceration, ulceration or infection; cleanliness of the palm, ease of cleaning and nail trimming; and the effect of hygiene-related disability on other areas of functioning. This assessment is a part of disability assessment scale (DAS). The score ranges from 0 to 3 based on the severity of the maintaining the hand hygiene.
6. A review of analgesics required from patient or caregiver.
7. We will record a video while we are doing the clinical assessment. These videos will be used by [name] for training purposes. During the recording the face will be excluded with a barrier. Any other recognizable marks such as any tattoos will be blurred to maintain the privacy and security of the patients . All patients would have already had this done with their nerve blocks before the procedure. We will remind all patients not to say their names or anything that might identify them to maintain the privacy.

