**Recruitment:**

a) [name], as a physiatrist with expertise in neurorehabilitation of chronic neurological conditions that results in spasticity, will inform all prospective patients that

Effect of the cryoneurolysis on pain and positioning in patients with wrist and hand contracture.

Protocol: [H22-03181]

Version 1.1

Jan 9,2023

are already elected to undergo DNB and cryoneurolysis to advise them that the study is being conducted. With permission, patients or their legal representative will be contacted by the research assistant. The consent form will be offered to the patients when they are offered and selected to undergo a cryoneurolysis. The legal representative will be asked to help with consent process in participants who are physically or cognitively unable to consent. They can either consent at the time of first treatment or at their preference they will have several weeks to review and consider the desire to participate.

b) Recruitment of participants will be through spasticity clinic at Victoria General Hospital, where [name] offers DNB and cryoneurolysis to the patients, routinely, as a part of their standard care to manage pain and spasticity. As a member within the circle of care, he will approach participants regarding obtaining permission for RAs to initiate contact, as per above.

c) Prospective participants will be identified as per the point above.

d) Many of the patients are expected to come from Long Term Care Facilities. We will contact the facility to see if it is easier for our team to do an in facility follow up rather than arranging transport.

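### Follow-up visits are counted from enrolment rather than from cryoneurolysis, so an early follow-up score can precede the procedure it is meant to evaluate

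*Protocol*

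**What the plan says.** The Methods section gives the only assessment schedule: "The assessment will be done at baseline, 2 weeks, 1 month and 3 months after being enrolled in the study". It adds that assessments fall on the day of a clinic appointment, but does not say how those appointments relate to the procedure.

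The effects of interest start elsewhere. Objective 1 is the effect of cryoneurolysis on pain. Hypothesis 4 is that "The needs for pain medication will decrease after the procedure". Under Statistical Analysis, the paired comparison is described as "applicable to pre-treatment and post-treatment", and of the mixed models the protocol says "Such models derive individual parameter estimates for baseline function and change pursuant to nerve or surgical procedure".

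On the order of events, the Background says that "after a successful DNB to reduce pain and the muscle tone, a patient is offered cryoneurolysis", and Recruitment item a says "The consent form will be offered to the patients when they are offered and selected to undergo a cryoneurolysis". The next lines of item a let the patient consent at the first treatment or take several weeks to decide. Inclusion criterion 5 requires candidacy for cryoneurolysis, not that it has been done. Research Design says "This study will not interfere or change the patients' medical care".

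Statistical Analysis also refers to "intensive repeated measures data spanning the 4-month study period", whereas the last assessment in Methods is at 3 months.

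**The concern.** The schedule and the analysis have different time origins, and no sentence joins them. If patients are enrolled when they are selected and treated later, a score labelled 2 weeks may be taken 2 weeks after treatment, a few days after it, or before it.

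Two things are then at stake. First, a nominal early visit would mix patients at different times since the procedure, possibly including untreated ones, so the early effect is diluted. Second, the within-person trajectory that the mixed model is meant to estimate is blurred, because visit time is not time since treatment. Recoding time from actual dates could repair the time axis later. It cannot supply a 2-week post-procedure assessment that was never scheduled.

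The concern does not extend to baseline. The exclusion criteria rule out earlier cryoneurolysis on the affected side, so no claim is made that baseline follows treatment.

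**Working it through.** **Is the lag between enrolment and procedure fixed anywhere?**

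- Methods: the clock starts at enrolment.
- Recruitment, item a: consent is offered at selection, which is a decision and not the procedure. Consent at the first treatment is allowed but not required, and the text does not say whether that treatment is the diagnostic nerve block (DNB) or the cryoneurolysis.
- Inclusion criteria and Statistical Analysis: those recruited are candidates for the procedure or being considered for it.
- Research Design: care is unchanged, so the study does not set the procedure date.

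The lag is therefore neither stated nor capped. The protocol has no figure of its own to reproduce on this point: its n = 25 is a convenience sample.

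**Inputs.** Visit times of 2 weeks, 1 month and 3 months (Methods) and n = 25 (Statistical Analysis). The lag L is an assumption, shown over a range.

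**Thresholds.** 1 month = 30.44/7 = 4.35 weeks; 3 months = 91.31/7 = 13.04 weeks. Time since procedure = visit time since enrolment − L. A score is pre-treatment when this is negative, that is, when L exceeds 2, 4.35 or 13.04 weeks for the three visits in turn.

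| Assumed L (weeks) | 2-week visit | 1-month visit | 3-month visit |
|---|---|---|---|
| 0 | 2 | 4.35 | 13.04 |
| 1 | 1 | 3.35 | 12.04 |
| 3 | −1 | 1.35 | 10.04 |
| 6 | −4 | −1.65 | 7.04 |

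Entries are weeks since the procedure.

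**Dilution at the 2-week visit.** Assume no change before treatment and equal effects after it. If k of 25 patients are still untreated, the mean change is multiplied by 1 − k/25. Each such patient costs 1/25 = 4%; k = 5 costs 20%; k = 10 costs 40%.

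**Illustrative power.** For a two-sided 5% paired t-test with n = 25, let q = k/25 and let d be the standardised change among the treated, with the SD of change within the treated and within the untreated set to 1. Adding the spread between the two groups, the effective standardised change is (1 − q)d / √(1 + q(1 − q)d²). For d = 0.5 and q = 0.2 this is 0.4/√1.04 = 0.392. Power from the noncentral t distribution:

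| Assumed d | q = 0 | q = 20% | q = 40% |
|---|---|---|---|
| 0.5 | 67% | 47% | 29% |
| 0.6 | 82% | 61% | 38% |
| 0.8 | 97% | 83% | 57% |

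The protocol states neither d nor q. The table shows sensitivity and is not a forecast.

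**The case against.** The strongest reply is that the authors meant baseline to be the treatment day and worded it loosely. Recruitment item a expressly allows consent at the first treatment. If that means cryoneurolysis, enrolment and procedure coincide for those patients. The several weeks offered for reflection come before consent, so they do not create a lag after enrolment. The DNB is largely or wholly over by then, because candidacy already rests on the response to it. Visits follow clinic appointments, and the analysis is worded around the procedure.

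This stands in part. The text does not prove that any lag exists, and neither the sequence of DNB then cryoneurolysis nor the promise to leave care unchanged shows a wait. But same-day consent is optional and the term for it is ambiguous, so the two clocks may coincide for some patients without having to for any. Staff following Methods would count from enrolment.

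It can also be said that this is an exploratory pilot with no named primary time point, that the 2-week score has no special role, and that a mixed model can use actual dates. These points limit the consequence. They do not help where the early post-procedure visit was never held.

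The 4-month wording is a separate small inconsistency that may be loose text. It adds no evidence that visits precede treatment.

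**Conclusion.** The concern holds. The protocol sets a visit clock that differs from the origin of the effect it analyses and leaves the interval between them open. An early follow-up score can therefore be pre-treatment: the 2-week score for any lag above 2 weeks, and the 1-month score for any lag above about 4.35 weeks.

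The size of the bias cannot be found from the document. It is zero if everyone is enrolled on the procedure day. The 20% and 40% losses rest on assumed counts of untreated patients, no change before treatment and equal effects. The baseline to 3-month contrast survives any lag under about 13 weeks, with follow-up shortened by the lag. This should be fixed, but it does not undermine the whole study. Confidence is medium, because the authors may have intended the treatment day.

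**What to change.** In Methods, state that baseline is assessed before cryoneurolysis and that the follow-up assessments take place 2 weeks, 1 month and 3 months after it. Record the procedure date for every patient, and use time since the procedure as the time variable in the mixed model. Reconcile the 4-month study period in Statistical Analysis with the last assessment at 3 months.

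The cost is a short amendment. The four assessments stay the same and clinical care is not touched. A patient without a pre-procedure baseline would drop out of the change analysis, and a patient who enrols but never has the procedure would contribute no follow-up.
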